**Mayo Clinic**

**RECOVER: Phase 2 Randomized, Double-Blind Trial TREATing hospitalized patients with COVID-19 with Camostat Mesilate, a TMPRSS2 Inhibitor**

Amendment 3 – March 3, 2023

Summary of Changes	
Protocol section updated	Nature of change
Title Page	

• Updated Document History to reflect Version 3

Section 4.0, Test Schedule	

• Footnote 'o' added to allow remote monitoring after day 1 for patients discharged from the hospital

Section 7.0, Protocol Treatment	

• Section 7.1 updated to allow NG tube as a potential route for Camostat or Placebo

Section 8.0, Adverse Event (AE) Monitoring and Reporting	

• 8.4.1 updated to send reports to Ono

• 8.6 pregnancy reporting added

Section 9.0, Biospecimens	

• 9.1 Table updated allowing all specimen collection to be mandatory on day 1, optional on all other days

• 9.2 Mayo Clinic Florida will assemble kits for their site

• 9.2.6 Specimens that are drawn during the evening hours (Monday through Wednesday) can be shipped the next morning

• 9.3.2 Mayo Clinic Florida will store specimens and ship batch at end of study enrollment to Mayo Clinic Arizona

Section 11.0, Drug Information	

• 11.1.4 Updated to allow NG tube as a potential route for Camostat or Placebo

Section 13.0, Statistical Considerations and Methodology	

• 13.4 Primary analysis updated for clarification on minimizing loss to follow-up

• 13.7 Stopping rule updated to specify the stopping rule criteria will be evaluated separately for each treatment arm

Editorial and administrative changes have been made throughout the protocol but do not affect the scientific content or meaning.	

**Schema**

\*As the Standard of Care (SOC) is rapidly evolving, the control arm will be at the discretion of the treating physician and in accordance with institutional standards. Institutions will be responsible for obtaining SOC medications. The following SOC medications will not be provided by this study.

- Remdesivir
- Anticoagulation of hospitalized patients per institutional standard

## 1.0 Background

COVID-19 infections caused by SARS-CoV-2 have overwhelmed health care systems around the globe due to the profound respiratory failure that is characteristic of severe disease and which constitutes the primary reason for death. Immune responses to SARS-CoV-2 infection follow a two phase pattern. In the first phase, adaptive immune responses are protective and lead to mild disease. However, if immunity is impaired or otherwise deficient, severe cases are associated with Lymphopenia and a cytokine storm at which point the immune response is maladaptive and leads to acute respiratory distress syndrome (ARDS) and pulmonary failure.

COVID-19 is a Coronavirus that is similar to the pathogen (SARS-CoV) which caused the SARS epidemic of 2002-2003. Research into SARS-CoV demonstrated the potential role of TMPRSS2 in the pathogenicity of that disease and in particular the link to pulmonary manifestations. Previous work has shown that the SARS S (spike) protein is proteolytically processed by TMPRSS2. SARS S is cleaved into several fragments upon coexpression of TMPRSS2 (cis-cleavage) and upon contact between SARS S-expressing cells and TMPRSS2-positive cells (trans-cleavage). SARS S protein is associated with inhibition of antibody mediated neutralization of the virus, and thus promotes viral spreading. TRMPSS2 is also a coreceptor for SAR-CoV (with ACE2), and is thus associated with SARS-CoV infectivity, shedding, and resistance to protective antibodies. Like SARS, SARS-CoV-2 has been shown to use the ACE2 and TMPRSS2 receptors for cell entry.

Camostat is a serine protease inhibitor that is currently approved in Japan for the treatment of chronic pancreatitis and reflux esophagitis. It exhibits anti TMPRSS2 activity in cell line studies. Camostat successfully abrogated SARS S cleavage, inhibited cell entry, and decreased viral replication.

There is currently no proven therapy for COVID-19 infection. Multiple trials are currently active, with multiple agents having shown some promise based on small case series. These include hydroxychloroquine and azithromycin.

## 2.0 Goals

### 2.1 Primary Objective

To determine if the reduction in TMPRSS2 activity via direct inhibition with Camostat mesilate combined with standard of care (SOC) treatment will increase the proportion of patients alive and free from respiratory failure at Day 28 in SARS-CoV-2 as compared to SOC treatment with placebo.

### 2.2 Secondary Objectives include the following:

- 2.2.1 To determine if reduction in TMPRSS2 activity via direct inhibition with Camostat mesilate combined with SOC treatment will increase the proportion of patients alive and free of ventilator use or ECMO at Day 28 as compared to SOC treatment combined with placebo.
- 2.2.2 To determine if the combination of Camostat mesilate combined with SOC treatment will result in a decreased mortality rate at 28 and 56 days as compared to SOC treatment combined with placebo.
- 2.2.3 To determine if time to clinical improvement is reduced in patients receiving SOC treatment combined with Camostat mesilate as compared to SOC treatment combined with placebo.
- 2.2.4 To determine if Camostat mesilate combined with SOC treatment is associated with overall improved clinical status at Days 14 and 28 as compared to SOC treatment combined with placebo.
- 2.2.5 To determine if Camostat mesilate combined with SOC treatment is associated with a reduced length of stay in the hospital as compared to SOC treatment combined with placebo.
- 2.2.6 To determine if Camostat mesilate combined with SOC treatment is associated with reduced duration of:
  - a) mechanical ventilation or ECMO use,
  - b) non-invasive ventilation or high-flow oxygen use, and

- c) supplemental oxygen use as compared to SOC treatment combined with placebo.
- 2.2.7 To compare the safety and toxicity profile of Camostat mesilate combined with SOC treatment as compared to SOC treatment combined with placebo.
- 2.2.8 To determine if treatment with Camostat mesilate combined with SOC treatment is associated with decreased incidence of thrombotic events and bleeding complications as compared to SOC treatment combined with placebo.

2.3 Exploratory Objectives

- 2.3.1 To determine changes in viral load over the course of treatment as determined by assays of nasopharyngeal secretions, oral secretions, stool, and serum.

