- e. Targeted physical examination will specifically target the pulmonary system, as well as any areas of concern from the medical history or noted on the prior physical examination or indicated by subject systems or other findings as determined by the Investigator or designee.
- f. BP, pulse rate, respiration rate, and temperature. Vital signs will be measured at Baseline, and twice daily at least 8 hours apart while hospitalized, and once daily as an outpatient. Timing of assessments in accordance with institutional SOP for hospitalized patients.
- g. See Appendix I for a list of specific CBC with differential, comprehensive metabolic panel, renal profile, and urinalysis with microscopic tests.
- h. See Section 12.0 for description of scale.
- i. Collect nose or throat swab to measure for the presence or absence of SARS-CoV-2 by a PCR based COVID-19 test. The swabbing site (nose or throat) used for the Baseline evaluation should be maintained for all subsequent assessments of the study. If only one nostril will be sampled, use the same nostril for collections.
- j. SpO2 determined by pulse oximetry with simultaneous recording of FiO2 to be recorded twice daily at least 8 hours apart while hospitalized, and once daily as an outpatient. Timing of assessments in accordance with institutional SOP for hospitalized patients.
- k. A + 3 day window will be allowed.
- l. Patients who are discharged prior to Day 14 will not need to come into the clinic to follow Day 1-14 Test Schedule. Patients will be called by Study Team for remote evaluation and will resume visits on Day 14 unless needing to be seen sooner.
- m. Assess as clinically indicated by the treating physician.
- n. Stool samples can be  $\pm$  1 day and will be collected only if patient is able to produce.
- o. Since patients may improve and be discharged from the hospital at any point during the study period, remote monitoring without an in-person exam may be utilized for all Physical exam and assessments after day 1 in accordance with institutional SOP.

R Research Funded

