## 9.0 Biospecimens

### 9.1 Summary Table of Research Blood/Blood Products to Be Collected for This Protocol

	Specimen Purpose	Mandatory or Optional	Blood or Body Fluid being Collected	Type of Collection Tube (color of tube top)	Volume to collect per tube (# of tubes to be collected)	Day 1	Day 7	Day 14	Day 28	Day 56	Process at site? (Yes or No) 
-C1	 Correlative  Banking	Mandatory on day 1, optional all other days	Nasal Pharyngeal	Swab	1	X	X	X	X	X	N
-C2	 Correlative  Banking	Mandatory on day 1, optional all other days	Whole blood	SST (red and black marble top)	8.5mL (1)	X	X	X	X	X	N
C3 	 Correlative  Banking	Mandatory on day 1, optional all other days	Stool	Brown and white bottle	25mL	X	X	X	X		N
-C4	 Correlative  Banking	Mandatory on day 1, optional all other days	Saliva	Oragene	1	X	X	X	X		N

	Specimen Purpose	Mandatory or Optional	Blood or Body Fluid being Collected	Type of Collection Tube (color of tube top)	Volume to collect per tube (# of tubes to be collected)	Day 1	Day 7	Day 14	Day 28	Day 56	Process at site? (Yes or No) 
-C5	 Correlative  Banking	Mandatory on day 1, optional all other days	PBMC, plasma	Na Heparin (green top)	10mL	X				X	N

1. All samples will be processed and stored by Arizona BAP.
2. All Mayo sites using RLIMS must add MCA processing instructions to RLIMS builds.
3. Stool samples can be  $\pm$  1 day and will be collected only if patient is able to produce.

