### 13.3.3 Exploratory Endpoint(s)

**1. Time to Viral Clearance:** Viral clearance will be assessed at days 1, 7, 14, 28, 56 after study entry and the proportion of patients having viral clearance at each of these days will be estimated as the proportion of patients who are documented as having non-detectable

viral shedding divided by the total number of patients in each treatment arm. Serum and nasopharyngeal assays will be used for this analysis.

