#### Exploratory Analysis

**Time to Viral Clearance:** Viral clearance will be assessed at days 1,7, 14, 28 and 56 after study entry and the viral clearance rate at each of these days will be estimated as the proportion of patients who are documented as having non-detectable viral shedding divided by the total number of patients in that treatment arm. The rates at each time point will be compared using chi-square tests to assess differences between treatment arms

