### 13.6 Sample Size

Randomization will be done according to a 1:1 ratio. Based on data from Wang et al, 82% of patients treated with Remdesivir were alive and free from respiratory failure at day 28. In the preliminary report of Remdesivir for the treatment of COVID-19 in 1059 hospitalized patients, approximately 70% of patients treated with Remdesivir were alive and free from respiratory failure at Day 15; Day 28 data are not yet available. Using an expected proportion of 80% for the SOC control arm, this study would require 132 patients in each arm (total of 264 patients). Sample sizes of 132 in each arm achieves 80% power to detect a difference between the group proportions of 12% for the primary endpoint. The proportion in the treatment arm is assumed to be 80% under the null hypothesis and 92% under the alternative hypothesis. The proportion in the SOC arm is 80%. The test statistic used is the two-sided Z-Test with unpooled variance. The significance level of the test is 0.05 (two-sided).

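### The virology objective asks for change in viral load in four sample types, but the plan analyses only per-visit non-detectability in two of them and does not use Day 1 as a baseline

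*Combined protocol and SAP*

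**What the plan says.** Section 2.3 holds one exploratory objective, 2.3.1: "To determine changes in viral load over the course of treatment as determined by assays of nasopharyngeal secretions, oral secretions, stool, and serum". It concerns a quantity, its change, and four sample types.

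The matching endpoint in 13.3.3 is labelled as a time to viral clearance, but it is defined as a proportion at each visit and limited to two sample types: "Serum and nasopharyngeal assays will be used for this analysis". The Exploratory Analysis paragraph under 13.5 repeats the visit days, "Viral clearance will be assessed at days 1,7, 14, 28 and 56 after study entry", counts patients "documented as having non-detectable viral shedding divided by the total number of patients in that treatment arm", and names the test: "The rates at each time point will be compared using chi-square tests to assess differences between treatment arms".

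Sections 4.0 and 9.1 schedule saliva and stool on Days 1, 7, 14 and 28. Every specimen type in 9.1 is "Mandatory on day 1, optional all other days". The only PCR readout described is qualitative (4.0, footnote i): "Collect nose or throat swab to measure for the presence or absence of SARS-CoV-2 by a PCR based COVID-19 test".

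**The concern.** An objective about change in load should lead to an estimate of change in load, and here none is planned. Four consequences follow from the text, and all would hold even if every sample were obtained.

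1. No parameter measures load or its change. Day 1 is one of the five cross-sectional rates, but it is not a baseline: there is no change score, no covariate, and no restriction to patients who had detectable virus at the start.
2. Saliva and stool enter no analysis, although Day 1 collection is mandatory and willingness to give the mandatory specimens is an entry criterion (3.1.9).
3. A patient undetectable on Day 1 in a given sample type, and still undetectable later, counts as cleared although nothing was cleared. The Day 1 comparison, at first dose, can show only baseline imbalance.
4. Separate daily proportions do not give a time to clearance.

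Reduced cell entry and viral replication are the drug's stated rationale (1.0, 11.1.1), and this is the only planned antiviral readout. If the primary result is null, a coarse readout makes it harder to tell a drug with no antiviral effect from one that lowers load without clinical benefit.

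**Working it through.** **Step 1: objective against analysis.**

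| Element | Objective 2.3.1 | Sections 13.3.3 and 13.5 |
|---|---|---|
| Variable | viral load | detectable or not |
| Contrast | change over treatment | rate at each day |
| Sample types | nasopharynx, mouth, stool, serum | nasopharynx, serum |
| Role of Day 1 | start of the course | one more tested day |
| Model | none named | unadjusted chi-square per day |

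The mismatch needs no assumption.

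**Step 2: the plan's own figure.** The only power statement (13.6) is "Sample sizes of 132 in each arm achieves 80% power to detect a difference between the group proportions of 12% for the primary endpoint". With 80% v 92%, two-sided 0.05 and unpooled variance, n = (1.960 + 0.842)² × (0.80×0.20 + 0.92×0.08) / 0.12² = 127.3, so 128 per arm. Power at 132 is 81.4%. The stated 80% reproduces to within 2 points. It says nothing about virology, for which the documents give no effect, SD, detection limit, clearance rate or correlation. Everything below is therefore illustration.

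**Step 3: cost of dichotomising, closed form.** Assume normal log10 load, SD 1.8 and effect -0.6, a shift of 0.6/1.8 = 0.333 SD, with 132 per arm.
- Clearance, 50% of controls undetectable: the camostat rate is Φ(0.333) = 63.1%. Power = Φ[(0.131×√132 − 1.96×√(2×0.565×0.435)) / √(0.25 + 0.631×0.369)] = Φ(0.18), about 57%.
- Load, unadjusted and ignoring the detection limit: Φ(0.333×√66 − 1.96) = Φ(0.75), about 77%.
- Load adjusted for Day 1 with correlation 0.5: the shift becomes 0.333/√(1 − 0.25) = 0.385, and power is Φ(0.385×√66 − 1.96) = Φ(1.17), about 88%.

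**Step 4: with a detection limit, by simulation.** Same inputs, values below the limit set to half the log10 limit, correlation with Day 1 of 0.3 to 0.7.

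| Per arm | Controls undetectable | Chi-square | Day-1-adjusted ANCOVA |
|---|---|---|---|
| 132 | 13-50% | about 43-60% | about 69-96% |
| 132 | 80% | about 43-45% | about 45% (corr. 0.3) to 54% (0.7) |
| 132 | 90% | about 29-30% | about 29% (0.3) to 32% (0.7) |
| 66 | 13-50% | about 24-35% | about 40-76% |

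The ANCOVA advantage is largest when few patients are undetectable and the correlation is high. It almost disappears once most patients have cleared.

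**Step 5: patients undetectable on Day 1.** Assume later clearance of 50% v 65% among patients detectable on Day 1. If a share d is undetectable on Day 1 and counted as cleared, the rates are d + (1 − d)×0.50 and d + (1 − d)×0.65. At d = 20% they are 60% and 72%: the 15-point difference becomes 12, and power at 132 per arm is 54%. Restricting to the 0.8×132 ≈ 106 per arm detectable on Day 1 restores the 15 points and gives 60%. The real value of d is unknown.

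**The case against.** **Day 1 is used.** A reader might infer that the analysis leaves the Day 1 value out. It does not: Day 1 is a listed analysis day. What is missing is its use as a baseline.

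**The objective is partly met.** A reader might infer that 2.3.1 goes wholly unanswered. Serial detectability at five days gives a coarse viral course in two sample types. The objective also names no comparison between arms, although 13.5 does plan one. This stands.

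**The power gain rests on invented inputs.** This also stands. No document figure fixes the size, and at 80-90% undetectable the gain is small or absent. Part of it comes from adjustment rather than quantification: at 50% undetectable and correlation 0.7, chi-square has 57%, logistic regression of clearance on Day 1 load 72%, and ANCOVA 84%, so 15 of the 27 points come from adjusting. The documents do not support saying that the plan would miss an antiviral effect.

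**A quantitative assay may not exist.** The PCR in 4.0 reads presence or absence, and no quantitative assay or detection limit is described. Objective 2.3.1 presupposes one, but the cost cannot be assumed to be wording alone.

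**Day 1 negatives may be few.** A PCR test is scheduled at baseline. But a positive result on it is not an entry criterion, and 3.1 limits neither the age of the confirming test nor symptom duration. The problem remains possible, with unknown frequency.

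**It is only exploratory.** True. No primary or secondary endpoint, sample size, interim boundary or safety rule depends on it. That limits the weight of the point but does not remove the mismatch.

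**Conclusion.** The point holds as a mismatch between objective and analysis. If the plan is followed exactly, load change is not estimated, saliva and stool go unanalysed, patients undetectable on Day 1 are not separated from those who clear virus, one of the five tests can show only baseline imbalance, and the endpoint's name does not fit its method. Objective 2.3.1 is answered partly and coarsely.

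The direction of the power loss is sound for visits where many patients still have detectable virus. Its size depends on the assumed SD, effect, normality and correlation in steps 3 and 4, and no gain should be claimed where most patients have cleared. The primary analysis is not touched.

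**What to change.** In 13.3.3 and 13.5:

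- Analyse log10 viral load (or cycle threshold) at Days 7 and 14 by ANCOVA or a mixed model, with the Day 1 value and the age and severity strata as covariates and values below the limit treated as left-censored.
- Name nasopharyngeal Day 7 as the lead comparison. Treat the other sample types and days as descriptive, so that four sample types at two days do not become eight competing tests.
- Keep clearance as a supporting summary among patients detectable on Day 1 in that sample type, adjusted for Day 1 load where available.
- Drop the Day 1 between-arm test and rename the endpoint.
- Report the number sampled by arm and day. Samples after Day 1 are optional and patients discharged early need not return before Day 14 (4.0, footnote l), so Day 7 samples may come mainly from those still in hospital. Reporting the counts exposes this selection but does not remove it.

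Condition: confirm that the research samples will have a quantitative readout. For any sample type without one, reword 2.3.1 to detectability and still apply the Day 1 restriction.

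Cost: no new patients, visits or samples; some extra analysis, and left-censoring to handle. If quantitative assays are not already planned, there is laboratory work as well, which the documents do not allow one to price.

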### **3.0 Patient Eligibility**

#### 3.1 Inclusion Criteria

- 3.1.1 Laboratory confirmed SARS-CoV-2 infection
- 3.1.2 Admitted to hospital for management of SARS-CoV-2
- 3.1.3 Age  $\geq 18$
- 3.1.4 Subject or legal representative able to give informed consent
- 3.1.5 Ability to take all study drugs
- 3.1.6 Respiratory status of 3 or greater on the WHO ordinal scale
- 3.1.7 ALT or AST  $\leq 5 \times$  ULN
- 3.1.8 Creatinine clearance  $\geq 50$  mL/min using the Cockcroft-Gault formula
- 3.1.9 Willingness to provide mandatory specimens for correlative research and banking (see Section 6.0 and 9.0).

#### 3.2 Exclusion Criteria

- 3.2.1 Women who are pregnant or breastfeeding
- 3.2.2 Known hypersensitivity to the study drug, the metabolites or formulation excipient

## 4.0 Test Schedule

	Baseline/Prior to Registration	Randomized Treatment Period (Day 1-Day 14)			Follow-Up Evaluation	
		Day 0 ( $\leq 2$ days)	Day 1 (1 st Dose)	Day 2-13 (l)	Day 14	Day 28 (k)
Informed Consent (a)	X					
Complete medical and surgical history	X					
Update of medical history	X					
Record medications and therapies (b)	X					
Record Concomitant medications		X	X	X	X	X
Height (c)	X					
Body weight	X			X		
Comprehensive physical examination (d), (o)	X			X	X	X
Targeted physical examination (e), (o)	X		X	X		
Vital Signs (f), (o)	X	X	X	X	X	X
12-Lead ECG	X			X		
Chest CT					X	X
CBC with differential (g)	X			X	X	X
Comprehensive metabolic panel (g)	X			X	X	X
Procalcitonin, IL-6, ferritin, azotemia, Ca, triglycerides, glucose, LDH, GGT, CPK, D-dimer, PT/INR, fibrinogen, and troponin		X		X	X	X
Thrombotic Events (m)			X	X	X	X
Renal profile (g)	X		X	X	X	X
Urinalysis with microscopic (g)	X			X		
Serum pregnancy test for WCBP	X				X	X
Urine pregnancy test for WCBP	X					
Ordinal Scale Assessment (h)	X		X	X	X	X
PCR based COVID-19 test (i)	X		Only Day 7	X	X	X
SpO2 by pulse oximetry with FiO2 (j)	X	X	X	X	X	X
Blood sample for future analysis (See Section 9.0) R		X	Only Day 7	X	X	X
Blood Sample for GBPA (See Section 9.0) R		X	Only Day 7	X	X	X

Stool (See Section 9.0) n, R		X	Only Day 7	X	X	
Saliva (See Section 9.0) R		X	Only Day 7	X	X	
PBMC (See Section 9.0) R		X				X
Nasal Pharyngeal (See Section 9.0)		X	Only Day 7	X	X	X
Adverse Event Evaluation		X	X	X	X	X

- a. ICF must be signed prior to performing Baseline evaluations.
- b. Record medications and therapies taken or received within 30 days prior to Baseline (or longer for investigational drugs for which 5 half-lives of the drug exceed 30 days).
- c. If subject is able to stand.
- d. Comprehensive physical examination will include the following organ or body system assessments: skin; head, eyes, ears, nose, and throat; thyroid; lungs; cardiovascular; abdomen (liver, spleen); lymph nodes; and extremities, as well as an abbreviated neurological exam.
- e. Targeted physical examination will specifically target the pulmonary system, as well as any areas of concern from the medical history or noted on the prior physical examination or indicated by subject systems or other findings as determined by the Investigator or designee.
- f. BP, pulse rate, respiration rate, and temperature. Vital signs will be measured at Baseline, and twice daily at least 8 hours apart while hospitalized, and once daily as an outpatient. Timing of assessments in accordance with institutional SOP for hospitalized patients.
- g. See Appendix I for a list of specific CBC with differential, comprehensive metabolic panel, renal profile, and urinalysis with microscopic tests.
- h. See Section 12.0 for description of scale.
- i. Collect nose or throat swab to measure for the presence or absence of SARS-CoV-2 by a PCR based COVID-19 test. The swabbing site (nose or throat) used for the Baseline evaluation should be maintained for all subsequent assessments of the study. If only one nostril will be sampled, use the same nostril for collections.
- j. SpO2 determined by pulse oximetry with simultaneous recording of FiO2 to be recorded twice daily at least 8 hours apart while hospitalized, and once daily as an outpatient. Timing of assessments in accordance with institutional SOP for hospitalized patients.
- k. A + 3 day window will be allowed.
- l. Patients who are discharged prior to Day 14 will not need to come into the clinic to follow Day 1-14 Test Schedule. Patients will be called by Study Team for remote evaluation and will resume visits on Day 14 unless needing to be seen sooner.
- m. Assess as clinically indicated by the treating physician.
- n. Stool samples can be  $\pm$  1 day and will be collected only if patient is able to produce.
- o. Since patients may improve and be discharged from the hospital at any point during the study period, remote monitoring without an in-person exam may be utilized for all Physical exam and assessments after day 1 in accordance with institutional SOP.

R Research Funded

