## 7.0 Protocol Treatment

7.1 Patients will be randomized to either the control arm (placebo) or the treatment arm (camostat).

**Control Therapy Placebo combined with SOC:** Patients will be randomized 1:1 to camostat or placebo taken as 2 tablets four times daily on an empty stomach at least 30 minutes before each meal, 2 hours since the last meal, and at bedtime. Remdesivir will be administered once daily IV for 5 or 10 days. Remdesivir must be obtained commercially. Remdesivir will not be supplied for this study. Other management decisions are left to the discretion of the treating physicians and may include any medicines deemed necessary and appropriate such as anticoagulation.

Agent	Dose Level	Route	Day
Camostat or placebo	200 mg four times daily on an empty stomach 30 minutes before each meal, 2 hours since last meal, and at bedtime	PO/NG €	1-14
Remdesivir¥	200 mg	IV	1
Remdesivir¥	100 mg	IV	2, 3, 4, 5 (5 day course) OR 2, 3, 4, 5, 6, 7, 8, 9, 10 (10 day course per local provider recommendation§)
Anticoagulation	Per institutional standard		

¥ The suggested dose is for adults and pediatric patients weighing  $\geq 40$  kg.

§ A treatment course of 10 days is recommended for adults and pediatric patients requiring invasive mechanical ventilation and/or extracorporeal membrane oxygenation. A treatment course of 5 days is recommended for adults and pediatric patients not requiring invasive mechanical ventilation and/or ECMO. If a patient does not demonstrate clinical improvement, treatment may be extended for up to 5 additional days (i.e. a total of 10 days).

€ Doses may be administered via NG tube by dissolving tablets in 55 ml of warm water until tablets dissolve into solution. Resulting solution can be administered via NG tube. Note, if a patient is on continuous tube feedings, camostat doses must be held.

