## 7.2 Dose Modifications

Treatment discontinuation in the event of investigator assessed treatment associated toxicity rather than dose reduction.

Missed doses should not be replaced. Rather, treatment should resume with the next scheduled dose. Doses missed due to clinical inability to administer the dose (e.g. patient is undergoing a procedure at the scheduled time) shall not be counted as a protocol deviation and should simply be recorded as “unable to give dose”.

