#### 11.1.6 Potential Drug Interactions: Camostat mesilate did not appreciably inhibit CYP1A2, CYP2C9, CYP2C19, CYP2D6 and CYP3A4 (in vitro).

#### 11.1.7 Known potential toxicities:

Clinically significant toxicities:

- Shock or anaphylactic symptoms
- Thrombocytopenia
- Hepatic function disorder or jaundice
- Hyperkalemia

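### No platelet count, ALT, AST or bilirubin is scheduled between baseline and Day 14, the last dosing day, although platelet and liver toxicity are named as clinically significant for camostat

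*Combined protocol and SAP*

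**What the plan says.** Section 11.1.7 names four clinically significant toxicities of camostat. Three of them show on a blood test: "Thrombocytopenia", "Hepatic function disorder or jaundice", and hyperkalemia.

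The Section 4.0 grid defines a "Randomized Treatment Period (Day 1-Day 14" and places the laboratory panels by column. Appendix I gives their content and ties them to the visits marked in that grid. Platelets are in the CBC. ALT, AST and total bilirubin are in the panel labelled "Comprehensive metabolic panel (g". The renal profile is a subset of that panel and includes potassium, but no liver test.

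Section 7.1 gives study drug on Days 1-14 ("200 mg four times daily on an empty stomach 30 minutes before each meal, 2 hours since last meal, and at bedtime"). Section 7.2 states the response to toxicity: "Treatment discontinuation in the event of investigator assessed treatment associated toxicity rather than dose reduction". For early discharges, footnote l of Section 4.0 says: "Patients who are discharged prior to Day 14 will not need to come into the clinic to follow Day 1-14 Test Schedule". The study team calls these patients instead, and they return on Day 14 unless they need to be seen sooner.

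**The concern.** One of the three laboratory-detectable toxicities, hyperkalemia, has a scheduled test within Days 2-13. The other two do not, and the documents give no reason for the difference.

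Three parts of the plan depend on toxicity being seen while patients are dosing:

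- the discontinuation rule in Section 7.2;
- the between-arm comparison of adverse events, including grade 3 or higher, in Section 13.5 item 9;
- the accrual-suspension rule in Section 13.7, which can be triggered at any time by grade 3 or higher events at least possibly related to treatment.

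A falling platelet count or rising aminotransferase without symptoms reaches any of these before Day 14 only if someone orders a test that the protocol does not call for. How often that happens depends partly on how long a patient stays in hospital, and length of stay is itself a secondary endpoint that camostat is hoped to reduce.

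**Working it through.** **Step 1. Fix the columns of the Section 4.0 grid.** In the text available for review, the second header row is shifted by one column and the Day 56 heading is lost. Read literally, it would put a CBC and metabolic panel mark under Days 2-13. Two internal checks rule that out:

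- The cells restricting a test to Day 7 stand in the third data column, so that column must be Days 2-13.
- PBMC is marked in the second and sixth data columns. The Section 9.1 table collects it on Day 1 and Day 56. Stool is marked in the second to fifth columns, and Section 9.1 gives Days 1, 7, 14 and 28.

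The six columns are therefore Baseline, Day 1, Days 2-13, Day 14, Day 28 and Day 56.

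**Step 2. Read the rows.**

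| Row | Relevant content | Baseline | Day 1 | Days 2-13 | Day 14 | Day 28 | Day 56 |
|---|---|---|---|---|---|---|---|
| CBC | Platelets | X | | | X | X | X |
| Metabolic panel | ALT, AST, bilirubin, potassium | X | | | X | X | X |
| Renal profile | Potassium | X | | X | X | X | X |
| Procalcitonin-to-troponin panel | GGT, PT/INR | | X | | X | X | X |
| Adverse event evaluation | | | X | X | X | X | X |

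**Step 3. Count the exposure before the first scheduled result.**

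- Planned doses: 14 days x 4 = 56.
- Doses on Days 1-13, with no scheduled platelets, ALT, AST or bilirubin: 13 x 4 = 52. Share: 52 / 56 = 92.9%.
- If the Day 1 GGT and PT/INR are counted as liver-related, the gap for any liver-related item is Days 2-13: 12 days, 12 x 4 = 48 doses, 48 / 56 = 85.7%. Day 1 is the day of the first dose, so those tests say little about toxicity that develops under treatment.

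**Step 4. Discharged patients.** Footnote l removes the Days 2-13 visits, and with them the renal profile. Section 7.1 sets dosing through Day 14 and does not say that it ends at discharge. A patient sent home early and still dosing therefore has no scheduled potassium, platelet or liver result until Day 14.

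**Step 5. Expected number of events.** Section 11 gives raised AST or ALT with camostat as at least 0.1% and below 0.5%. In an arm of 132:

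- 132 x 0.001 = 0.13 patients;
- 132 x 0.005 = 0.66 patients.

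This assumes that the listed rate carries over to hospitalized COVID-19 patients at this dose, which the documents do not address. Section 11.1.7 gives no frequency for thrombocytopenia or hepatic function disorder, so no count can be derived for those.

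**The case against.** The best defence is that this is a sparse laboratory grid by choice, and that detection does not rest on it alone. Several parts of that stand:

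- Day 14 is a dosing day with both panels marked. Adverse events are evaluated throughout, and discharged patients can be seen sooner. Section 8.5.2 requires grade 3 and 4 events to be reported whatever their attribution, so a graded abnormality found in routine care is captured. Section 13.7 adds weekly review and a DSMB. A reader might infer that the plan cannot detect these toxicities during dosing; the documents do not support that.
- No two sections contradict each other outright. Section 11.1.7 sets no monitoring frequency, and Section 7.2 acts on the investigator's assessment rather than on a scheduled result. This is a mismatch between named risks and scheduled tests.
- A reader might infer that the adverse event comparison leans in camostat's favour. That needs camostat to shorten stay and the lost tests to contain reportable events. Both arms follow the same blinded schedule, and nothing in the documents fixes the direction or size.
- The Section 13.7 thresholds are 3 of the first 10 patients, then 30%, judged separately by arm. Missed events at the listed AST/ALT rate would hardly move them.
- The remdesivir aminotransferase rate in Section 11.3.7 is tempting as a yardstick. Remdesivir is background care available in both arms, so that rate does not measure camostat's toxicity.

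The defence does not explain why potassium is scheduled within Days 2-13 while platelets and liver tests are not. Nor does it say what applies to a discharged patient who is still dosing. Routine inpatient testing is plausible, but the protocol does not require it, and it ends at discharge.

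**Conclusion.** The concern holds in a limited form. Followed as written, the plan schedules no platelet count, ALT, AST or bilirubin on Days 1-13, which carry 52 of 56 planned doses. Until Day 14, symptomless platelet or liver toxicity enters the discontinuation decision, the adverse event comparison and the accrual-suspension rule only through routine-care or unscheduled testing. Ascertainment may differ between arms if length of stay differs; direction and size are unknown. At camostat's stated AST/ALT rate, fewer than one affected patient is expected in the camostat arm, so this should be corrected but does not threaten the trial's main conclusion.

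The conclusion rests on the column alignment in step 1, which the grid and the Section 9.1 table both support, and on reading Section 7.1 as continuing dosing after discharge because it states no end other than Day 14.

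**What to change.** Reconcile Section 4.0 and footnote l with Sections 7.2, 11.1.7 and 13.7 and Appendix I, so that platelet and liver results obtained during dosing are captured in the protocol data.

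For inpatients there are two inexpensive routes. Routine-care results from those days can be entered in the CRF. Alternatively, the draw already marked for the renal profile in Days 2-13 can be used: the liver tests belong to the fuller panel of which that profile is a part, and a CBC would have to be added for platelets. The Day 7 research blood draw is not a reliable vehicle, because Section 9.1 makes it optional.

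Footnote l should state what applies, potassium included, to discharged patients who are still dosing. The sponsor's clinicians should set the timing and any action levels; none is proposed here.

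The cost is a test-schedule amendment, some CRF entry and, if the sponsor chooses it, a local blood sample for discharged patients.
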